#### **Coagulation**:

Prothombin time	
INR (international normalized ratio)	Not applicable, because CTCAE grading includes the information about current anticoagulation
aPTT (activated partial thromboplastin time)	Yes ("Activated partial thromboplastin time prolonged")
Fibrinogen	Yes ("Fibrinogen decreased")
Quick test	No

#### 5.5 Statistical models

#### 5.5.1 Primary analysis

Proc logistic is used. The SAS code will be implemented in the TFL shells as programming note.

Rescue medication will be identified by the respective yes/no-items in the forms "Prior/Concomitant medication", "Procedures and Non-drug therapy", "WHO Bleeding Scale", "Dosage administration record for Eltrombopag", and "Dosage administration record for Dexamethasone". During the data review meeting the medication of each patient was reviewed and considered if the investigators' classification as rescue medication (yes or no) is reasonable. Unambiguous cases were overruled. For example when only the first episode but not the subsequent episodes were classified as a rescue medication by the investigator.

#### 5.5.1.1 Algorithm to derive the parameter "sustained response off treatment"

The parameter was assessed by the Data Review Committee, see data Review Meeting Minutes.

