6.4 Treatment blinding

Treatment will be open label to subjects, investigator staff, persons performing the assessments, and the clinical trial team.

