### 2.1.1 General definitions

**Study treatment** for patients randomized to the investigational combination treatment is eltrombopag until Week 26 in combination with 1 cycle of high-dose dexamethasone (subsequently referred to as treatment group ETB+DEX). For patients randomized to the control arm the study treatment consists of 1-3 cycles of high-dose dexamethasone (subsequently

referred to as treatment group DEX). These treatments will be called "study treatment" in the rest of the document.

When eltrombopag and/or dexame thas one will be given additionally, this is assessed as rescue or - if applicable - as concomitant medication during the data review meeting case-by-case.

The last available assessment on or before the date of start of eltrombopag is taken as "**baseline**" assessment. It is assumed that all assessments at Week 1/Day 1 are captured pre-dose on first day of eltrombopag (e.g. PROs), thus this Week 1/Day 1 is used for baseline when no screening values are available. Otherwise the screening values are considered as baseline. For all analyses on platelets the platelet count directly before pre-treatment will be used as baseline value in the pretreated patients. This is the more adequate way of taking into account the initial value at time of diagnosis and before pre-treatment for all patients

**Pre-treatment period**: from day of subject's informed consent to the day before first dose of study treatment.

**On-treatment period**: from date of first dose of study treatment to date of treatment discontinuation (including start and stop date).

**Treatment discontinuation** is the date of last study medication given as study treatment but not as rescue medication or not after after re-initiation, i.e. initial dose after failure of 1-3 DEX cycles (for details see Derivation of time point of treatment discontinuation5.1).

**Post-treatment period**: starting at day 30+1 after last dose of study treatment

The **Safety Follow-up period** specifies the observational period (30d) for which patients will be followed-up for safety events/measures.

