### 2.5 Analysis of the primary objective

#### 2.5.1 Primary endpoint

The primary objective is to compare the ability of both study treatments to induce sustained response off treatment at 52 Weeks.

The primary endpoint is the proportion of patients with sustained response off treatment at 52 weeks (i.e. until study visit Week 53).

Sustained response off treatment is defined as:

- reach platelet count  $\ge 30 \times 10^9$ /L and then maintain platelet counts  $\ge 30 \times 10^9$ /L after discontinuation of study treatment AND
- maintain platelet count  $\ge 30 \times 10^{9}$ /L in the absence of bleeding events  $\ge$  Grade II AND
- without the use of any rescue therapy (see Section 6.2.3 of CSP) until week 52

Details on Response or non-response are assessed during the Data Review Meeting and documented accordingly.

For the primary and supportive analyses the FAS will be used.

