The primary analysis will be performed comparing the treatment groups with respect to the primary efficacy outcome, based on the Odds Ratio, in a Logistic Regression model with the factor treatment and cofactors ITP-directed pre-therapy ("no" vs. "yes" during 3 days before randomization), screening platelet count (quantitative) and age ( $\leq$  vs. >60 yrs). The odds ratio and its 95% confidence interval (CI) and p-value will be given. The null hypothesis of equal odds will be rejected if the 2-sided p-value from the logistic regression model for the factor "treatment" is <0.05; however, superiority of eltrombopag in combination with a short course of dexamethasone will be claimed only if the direction is correct, i.e. if the odds of response are higher under eltrombopag plus a short course of high-dose dexamethasone compared to 1-3 cycles of dexamethasone monotherapy (ORB/A < 1)

In case the analysis result is revealed to be unstable / does not converge due to cells with too low numbers, the covariates age and ITP-directed pre-therapy may be removed, until valid results are seen. This will be checked during dry run preparation, i.e. before the data have been unblinded, to warrant avoidance of data-driven decision making. Furthermore, during this process, an analysis using an exact logistic regression model (StatXact) may be considered.

<sup>3 For pretreated patients the last platelet count before pre-treatment was started

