# 5 Appendix

### 5.1 Derivation of time point of treatment discontinuation

The time point of **treatment discontinuation** is the date of last dose of study medication given as study treatment but not as rescue medication, not after re-initiation or not after as initial dose after failure of 1-3 DEx cycles, and not as concomitant medication (if applicable).

For patients randomized to DEX monotherapy the time point of treatment discontinuation is the date of last study medication dexamethasone documented on the "End of Treatment" CRF. During the data review meeting it will be verified, that this date corresponds to the stop of study treatment but not to the stop of rescue medication.

For patients randomized to ETX+DEX combination therapy the time point of treatment discontinuation is the maximum date of the study medications eltrombopag and dexamethasone documented on the "End of Treatment" CRF, in general. When the primary reason for permanent discontinuation of eltrombopag is:

- "stop of eltrombopag re-initiated after relapse", or
- "stop of eltrombopag as rescue medication for patients randomized to DEX monotherapy" or
- the free text specification of "other reason" indicate that elthombopag was re-initiated or used after switch from DEX to ETB

the stop of study treatment eltrombopag has to be visually assessed from the data of the "Eltrombopag – Dosage Administration Form" during the data review meeting.

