#### 5.5.4 Duration of overall response

Overall response (OR) and time points reaching and loosing OR was assessed by the Data Review Committee, see data Review Meeting Minutes.

The following censoring rules are applied:

- If a patient does not loose overall response the duration is censored with the date of the last platelet assessment after Week 4
- If a patient does not respond initially by Week 4 (i.e. all platelet counts <30 G/L until Week 4) the interval is censored with 0 (days)

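### SAP 5.5.1.1 gives no derivation for sustained response off treatment and leaves the final call to a Data Review Committee whose masking is not stated, in an open-label trial of about 24 patients

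*SAP*

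**What the plan says.** Protocol 12.4.1 and SAP 2.5.1 define the primary endpoint by platelet count, bleeding grade and rescue. SAP 2.5.3 counts missing assessments and early dropout as non-response. SAP 2.5.1 then adds: "Details on Response or non-response are assessed during the Data Review Meeting and documented accordingly". SAP 5.5.1.1 is headed as an algorithm, but its whole content is: "The parameter was assessed by the Data Review Committee, see data Review Meeting Minutes".

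Several inputs to the endpoint are judged in the same forum:

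- **Extra study drug.** Under SAP 2.1.1, additional eltrombopag or dexamethasone is "assessed as rescue or - if applicable - as concomitant medication during the data review meeting case-by-case". SAP 2.4.2 adds that the committee decided which doses were rescue and which were study treatment.
- **Rescue flags.** SAP 5.5.1 names the eCRF forms that carry the investigators' yes/no items, then allows the meeting to revise them: "Unambiguous cases were overruled". It gives one example and no rule.
- **Stop date.** Under SAP 5.1, in three listed situations the end of study eltrombopag "has to be visually assessed from the data of the" dosing form at the meeting. For the dexamethasone arm the meeting verifies the CRF date.

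SAP 5.5.1.2, 5.5.4 and 5.5.5 treat eligibility for discontinuation and the timing of overall and complete response in the same way. For overall response, the "time points reaching and loosing OR was assessed by the Data Review Committee".

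On masking, Protocol 6.4 says: "Treatment will be open label to subjects, investigator staff, persons performing the assessments, and the clinical trial team".

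**The concern.** The primary variable cannot be reproduced from the SAP. A second statistician with the locked database and this plan would not know how to classify a patient whose status turns on an extra course of study drug or an unclear stop date.

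Such calls can decide the outcome. Arm B allows one to three dexamethasone cycles at intervals of 14 to 28 days. If a later course counts as study treatment, the discontinuation date moves to its last dose and response stays possible. If it counts as rescue, the patient is a non-responder under Protocol 6.2.3. That section also makes any ITP-directed therapy after discontinuation a non-response, whereas SAP 2.1.1 lets extra study drug be called concomitant and gives no criterion. The two need to be reconciled.

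The people making these calls work in an open-label trial from dosing records that partly reveal the arm. Knowledge of the arm could therefore influence individual calls, and with so few patients a single call is visible in the estimate.

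**Working it through.** **Inputs from the documents.** Protocol 12.8.1: assumed response 30% (dexamethasone, arm B) and 65% (combination, arm A), two-sided 5% level, 90% power, 47 per arm; after Amendment 3 about 24 patients in total and power of about 24%. At 1:1, 24 patients are 12 per arm.

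**Reproducing the plan's own figures.** With d = 0.35 and mean rate 0.475:

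n = [1.960 × √(2 × 0.475 × 0.525) + 1.282 × √(0.30 × 0.70 + 0.65 × 0.35)]² / 0.35² = 40.7, that is 41 per arm.

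With continuity correction: (40.7 / 4) × [1 + √(1 + 4 / (40.7 × 0.35))]² = 46.2, that is 47 per arm, as stated. Inverting the corrected formula at 12 per arm gives 24.3% power, which matches the stated 24%. These figures are not in dispute. They confirm the rates and sample size used below.

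**Effect of one call on a rate.** 1/12 = 8.3 percentage points in that arm.

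**Effect on the odds ratio.** The documents give no results, so responder counts are an assumption: 8/12 in arm A and 4/12 in arm B, the nearest whole patients to 12 × 0.65 = 7.8 and 12 × 0.30 = 3.6. The table shows changes in both directions. The odds ratio is A versus B, unadjusted; the plan writes B versus A, the reciprocal.

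| Change | A | B | Odds ratio | 95% Wald CI | Fisher p |
|---|---|---|---|---|---|
| None | 8/12 | 4/12 | (8×8)/(4×4) = 4.0 | 0.73–21.8 | 0.22 |
| One call for A | 9/12 | 4/12 | (9×8)/(3×4) = 6.0 | 1.02–35.4 | 0.10 |
| One call against A | 7/12 | 4/12 | (7×8)/(5×4) = 2.8 | 0.53–14.7 | 0.41 |
| One in each arm for A | 9/12 | 3/12 | (9×9)/(3×3) = 9.0 | 1.42–57.1 | 0.039 |
| One in each arm against A | 7/12 | 5/12 | (7×7)/(5×5) = 1.96 | 0.39–9.93 | 0.68 |

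The planned model adjusts for pre-therapy, screening platelet count and age, so the p-values only illustrate fragility.

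**Is the committee masked anywhere?** The nearest text is in SAP 2.5.2: "This will be checked during dry run preparation, i.e. before the data have been unblinded". It concerns convergence of the logistic model, not the responder calls. No text in either document masks the committee.

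**The case against.** The strongest reply is that the endpoint is rule-based already and the committee only applies the rules. The criteria are written, rescue is defined in Protocol 6.2.3, its eCRF sources are listed in SAP 5.5.1, the discontinuation date has a default in SAP 5.1, and missing data have a rule. SAP 2.5.4 sorts non-response into eight distinct categories by the first reason that applied. All of this stands. A reader might infer that response is decided by opinion with no rule behind it, and the documents do not support that. The gap is a missing programmable derivation together with discretion at the points listed above.

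A reader might also infer that every input is objective, so that a program could simply replace the committee. The SAP contradicts this. The End of Treatment date may belong to re-initiated or rescue eltrombopag, rescue flags may be inconsistent across episodes, and rescue in the treatment phase is defined partly by the aim of the therapy. Some judgement is needed.

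The one documented override would not change response status. The first episode was already flagged as rescue, so the patient is already a non-responder.

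SAP 2.5.4 also plans a platelet-only analysis that ignores bleeding, discontinuation, re-initiation and rescue, and so bypasses most of the disputed judgements. Rescue, dosing and bleeding are listed, which allows some audit. These are real safeguards. However, the platelet-only analysis answers a different question and cannot show what the committee's calls did to the primary result.

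Finally, the meeting minutes are not among the documents and may record decision rules. Rules kept only in minutes would still be outside the SAP.

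**Conclusion.** The point holds as a gap in derivation and transparency. Criteria exist, but the step from data to responder status is not written, and judgement on rescue classification, some stop dates and the final call sits with a committee of unstated masking in an open-label trial.

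At about 12 per arm, one call is worth 8.3 points in an arm's rate. On the assumed 8/12 versus 4/12, one call moves the unadjusted odds ratio within 2.8 to 6.0, and one call in each arm moves it within 1.96 to 9.0. The size rests on those assumed counts and on equal arms of 12.

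Two stronger readings go too far. The first is that the committee knew the arms and biased the result. The documents show that a shift was possible, not that one occurred, and knowledge of the arm is an inference from the open-label design and the dosing records. The second is that the harm lies in crossing p = 0.05. Since Amendment 3 all analyses are to be read descriptively, although SAP 2.5.2 still carries the superiority rule. The harm is to the credibility of the estimate.

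**What to change.** Write a programmable rule into SAP 5.5.1.1 from the existing criteria and use it for the primary analysis:

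- platelets of at least 30 × 10⁹/L reached, then maintained at all assessments from discontinuation of study treatment to Week 53;
- no bleeding of Grade II or higher;
- no rescue as defined in Protocol 6.2.3, taken from the eCRF items named in SAP 5.5.1;
- missing assessments or early dropout count as non-response, as in SAP 2.5.3.

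State the time window for bleeding and rescue. SAP 2.5.1 does not fix when it opens, while the first non-response category in SAP 2.5.4 counts events before discontinuation; the two must agree. Add a written data rule for the study-treatment stop date in the situations that SAP 5.1 now leaves to visual review. Without it, a rule that refers to 5.1 leads back to the meeting.

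Refer only cases the rule cannot settle to the committee, on listings without arm labels as far as feasible. This will not mask fully, because dosing records partly reveal the arm. List by arm every case where the committee departs from the rule or from the investigator's flag, and report the committee version as a sensitivity analysis.

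The cost is about a page of SAP text, a short program and one extra analysis. Sample size and power do not change, and the committee's work is kept.

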# 5.5.1.2 Algorithm to derive the parameter "eligible for treatment discontinuation"

The parameter was assessed by the Data Review Committee, see data Review Meeting Minutes

#### 5.5.2 Secondary analysis

#### 5.5.2.1 FACIT Fatigue

In this study FACIT Fatigue, version 4 is used to assess patient's fatigue. Each of the 13 items is scored 0 to 4 ("not at all" to "very much"). The FACIT score is calculated as follows:

Item responses HI7, HI12, AN1 to AN4, AN8, AN12 and AN14 to AN16 have to be reversed (4-item response). The reversed items and the responses for AN5 and AN7 have then to be added up. The resulting sum will be multiplied by 13 and divided by the number of answered items (resulting in a score range between 0 and 52). In case more than 6 questions are missing, fatigue cannot be calculated.

#### 5.5.2.2 SF-36 V2

Two SF36V2 summary scores are calculated: Physical and Mental Component Summary

The scoring is described in Ware JE, Kosinski M, Dewey JE. How to score Version 2 of the SF-36® Heatlth Survey.

SF-36V2 items and scales are scored so that a higher score indicates a better health state. For example, functioning scales are scored so that a high score indicates better functioning and the pain scale is scored so that a high score indicates freedom from pain.

The items and scales are scored in the following steps 4 steps:

1. Item recoding for the 10 items that require recoding (Range 0-5)

2. Computing raw scale scores by summing across items in the same scale (raw scale scores)

Physical functioning (PF): Questions 3a to 3j, no recoding Role-Physical (RP): Questions 4a to 4d, no recoding Bodily pain (BP): Questions 7+7, recoding o both items General health (GH): Questions 1, 11a-11d, recoding of Item 1, 11b and 11d Vitality (VT): Questions 9a, 9e, 9g, 9i, recoding of item 9a and 9e Social functioning (SF): Questions 6 and 10, recoding ot item 6 Role-emotional (RE): Question 5a to 5c; no recoding Mental Health (MH): Questions 9b, 9c, 9d, 9f, 9h, recoding ot item 9d and 9h Reported health transition (HT): question2, no recoding

Formular for transformation of raw scale scores to 0-100 scale scores

Transformed scale =  $\frac{(Actual \ raw \ score - lowest \ possible \ raw \ score)}{Possible \ raw \ score \ range} * 100$ 

- 3. Transforming raw sale scores to a 0-100 scale (transformed scale scores), using the means and standard deviations of 1998 general U.S. Population
- 4. Transforming 0-100 scales scores to have a mean of 50 and standard deviation of 10 (norm-based scale scores)
- 5. Aggregation of Scale scores in aggregate physical and mental component scores

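### The SAP's SF-36v2 scoring list counts Question 7 twice for Bodily Pain and assigns Question 8 to no scale, and it ties the population norms to a step that uses none

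*SAP*

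**What the plan says.** SAP 5.5.2.2 refers to the published SF-36v2 scoring manual and then sets out the scoring itself. It states that "Two SF36V2 summary scores are calculated: Physical and Mental Component Summary".

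The first step is given as "Item recoding for the 10 items that require recoding (Range 0-5", and the second sums items within each scale. Bodily Pain is "Bodily pain (BP): Questions 7+7, recoding o both items". Four other scales also have recoded items:

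- General Health has three such items, in the entry "General health (GH): Questions 1, 11a-11d, recoding of Item 1, 11b and 11d".
- The Vitality scale has four items, and the first two of them are recoded.
- Social Functioning has one such item, in the entry "Social functioning (SF): Questions 6 and 10, recoding ot item 6".
- The Mental Health scale has five items, two of which (9d and 9h) are recoded.

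The printed 0-100 formula subtracts the lowest possible raw score from the actual raw score, divides by the possible raw score range and multiplies by 100. Step 3, which applies this formula, is said to be done "using the means and standard deviations of 1998 general U.S. Population". Step 4 rescales to mean 50 and SD 10 and names no reference population. Step 5 aggregates the scales into the physical and mental component scores. The section announces four steps and lists five.

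Protocol 12.5.1 (item 9) and SAP 2.7.1 (item 8) promise the change in each domain score. Protocol 8.5.1 names Bodily Pain as one of the eight domains and says that scoring is norm-based.

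**The concern.** A question added to itself is not a two-item scale. On a literal reading, Bodily Pain carries only the answer to Question 7, and an answer collected from every patient is never used. Because domain scores are reported, Bodily Pain is an output in its own right as well as an input to the component scores.

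The norm reference looks misplaced. Step 3 is a pure range transformation and has no use for population means and SDs. Step 4 cannot be carried out without them and is silent on where they come from.

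This section is the SAP's own scoring specification. Two programmers working independently from the same text could make the same mistake and agree with each other. A check that merely counts recoded entries would also pass, because Question 7 entered twice still fills two places.

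**Working it through.** **Inputs.** The item list, the recoding statements and the 0-100 formula are all from SAP 5.5.2.2. The documents' readable text gives no response range for the pain items, so the ranges in step 3 below are assumptions.

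**1. Reproducing the SAP's count of 10.**

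| Scale | Questions | Distinct items, as written | Recoded, as written | Distinct items, with 7 and 8 | Recoded, with 7 and 8 |
|---|---|---|---|---|---|
| Physical Functioning | 3a-3j | 10 | 0 | 10 | 0 |
| Role Physical | 4a-4d | 4 | 0 | 4 | 0 |
| Bodily Pain | 7+7 | 1 | 1 | 2 | 2 |
| General Health | 1, 11a-11d | 5 | 3 | 5 | 3 |
| Vitality | 9a, 9e, 9g, 9i | 4 | 2 | 4 | 2 |
| Social Functioning | 6, 10 | 2 | 1 | 2 | 1 |
| Role Emotional | 5a-5c | 3 | 0 | 3 | 0 |
| Mental Health | 9b, 9c, 9d, 9f, 9h | 5 | 2 | 5 | 2 |
| Health transition | 2 | 1 | 0 | 1 | 0 |
| Total | | 35 | 9 | 36 | 10 |

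As written, the list has 36 places but 35 distinct items, and 1 + 3 + 2 + 1 + 2 = 9 distinct recoded items. The stated 10 is reached only with two different pain questions: 2 + 3 + 2 + 1 + 2 = 10.

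**2. Which question is missing.** The list covers Questions 1 to 7 and 9 to 11. The only gap from 1 to 11 is Question 8. That it is the second pain item is inferred from this gap and from the count, because its questionnaire page is not in the text available for review.

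**3. Size of the error in Bodily Pain.** Let both recoded items run from a to b (assumption). The lowest possible raw score is 2a and the range is 2(b - a).

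- Literal score: 100 × (2·Q7 - 2a) / (2(b - a))
- Intended score: 100 × (Q7 + Q8 - 2a) / (2(b - a))
- Error: 100 × (Q7 - Q8) / (2(b - a))

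| Assumed range | Error per level of difference | Largest error |
|---|---|---|
| 1 to 5 | 100 / (2 × 4) = 12.5 points | ±50 points |
| 1 to 6, or 0 to 5 | 100 / (2 × 5) = 10 points | ±50 points |

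The largest error arises when the answers differ by the full range: 100 × (b - a) / (2(b - a)) = 50. When Q7 = Q8 the error is zero. With 12 patients in an arm, the scenario in the protocol's Amendment 3 rationale, a one-level difference in one patient moves the arm mean by 10/12 = 0.8 to 12.5/12 = 1.0 points. The error in a change from baseline is the difference between the errors at the two visits, so it cancels where the gap between the two answers is the same at both.

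**4. Norms.** The step 3 formula contains only the actual score, the lowest possible score and the range, so the misplaced norm phrase does not alter the 0-100 score. Step 4 needs a reference mean and SD for each scale and names no source.

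**5. Item range.** The SAP gives 0-5 for the recoded items. In the questionnaire in Protocol Appendix 3 (Table 16-4), the nine items on feelings have answers numbered 1 to 5. By number and order they match 9a to 9i, of which 9a, 9d, 9e and 9h are recoded. The 0-100 formula depends on the lowest possible raw score, so the stated range needs checking.

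**The case against.** The strongest reply is that this is a typing slip in a summary of an external manual. The SAP says that the manual describes the scoring. The Bodily Pain line speaks of both items being recoded, and the count of 10 fits only two different questions. The section has many other slips of the keyboard. Nothing shows that the program follows the slip. All of this stands, and it identifies the intended text, but the written specification remains wrong and an entry count would not expose it.

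A reader might infer that Bodily Pain and both component scores will certainly be wrong. The documents do not support that. The error depends on literal programming and affects only patients whose two pain answers differ. The SAP also gives no weights and does not say which scales enter which component score, so the error can be traced only to any component score that uses Bodily Pain.

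A reader might also infer that step 4 would be standardised to the trial's own data, or visit by visit, so that comparability is lost. No text suggests this. Step 4 is labelled norm-based, the protocol says the same, and the 1998 U.S. norms in the line above are the only ones named.

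It is fair to add that SAP 2.11 plans descriptive statistics only for SF-36, and that Protocol 12.8.1 makes all analyses descriptive with about 24 patients expected.

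**Conclusion.** The scoring specification is wrong as written on two points. Bodily Pain repeats Question 7 and leaves Question 8 unassigned, which contradicts the SAP's own count of recoded items (9 against 10). The norm reference sits at a step that cannot use it and is absent from the step that needs it.

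If the list is programmed literally and both pain items share a range, the 0-100 Bodily Pain score is off by 10 to 12.5 points per level of difference between the two answers. It is off by at most 50 points, and not at all where they agree. The effect on the component scores cannot be computed from the documents.

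The misplaced norm phrase need not change any score by itself; what it leaves open is the reference for step 4. The 0-5 item range is a point to verify and is not shown to be wrong for the pain items, whose response range is not available. The finding concerns a secondary, descriptive outcome and does not touch the primary analysis.

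**What to change.** In SAP 5.5.2.2:

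- Replace the Bodily Pain entry with *Bodily pain: Questions 7 and 8, both recoded*.
- Move the reference to the 1998 U.S. means and SDs from step 3 to step 4.
- Change the announced number of steps from four to five.
- Check the stated item range of 0-5 against the questionnaire and correct it if it does not match.
- Confirm that the scoring program reads Question 8. A count of recoded entries is not enough.

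The cost is a few wording corrections and one program check. No new data are needed. If outputs have already been produced from a literal reading, Bodily Pain and any component score that uses it should be rerun.
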